5.1.4. Description and pre-clinical experience of ChAdOx1 and ChAdOx1 85A

ChAdOx1 85A is an adenoviral vaccine based on a vector that is a chimpanzee adenovirus isolate Y25 expressing the *M.tb* antigen 85A [51]. Adenoviruses are attractive candidates for use as viral vectors and have been used as vaccine vectors for a number of conditions; however, the use has been limited by the high level of anti-vector immunity present in humans in whom adenovirus is a ubiquitous infection. This has led to the consideration of simian adenoviruses, which are not known to cause pathology or illness in humans and to which the prevalence of anti-vector antibodies is low. The ChAdOx1 vector has been developed by the University of Oxford and been used with different inserts for vaccination, for example the vaccine ChAdOx1 NP+M1 has demonstrated an excellent safety profile in the Influenza trial FLU004. A BCG – ChAdOx1 85A – MVA85A prime boost regime is more protective than BCG alone in mice [22].

As TB034 was a first in man trial for ChAdOx1 85A a lower dose of 5 x 10⁹ vp was administered initially, with dose escalation post safety review as follows. The first six volunteers in the study received 5 x 10⁹ vp of ChAdOx1 85A. Their data was deemed to have an acceptable AE profile at review, and so the dose was escalated to 2.5 x 10¹⁰ vp ChAdOx1 85A.

Immunogenicity

A single dose of 2.5x10¹⁰ vp of ChAdOx1 85A induced significant Ag85A-specific IFN- γ responses following vaccination in the three study groups, these responses peaked 14 days post-vaccination (Wilcoxon test, $p=0.0005$ for Groups A (ChAdOx1 85A alone), B (ChAdOx1 85A – MVA85A) and C (ChAdOx1 85A – ChAdOx1 85A – MVA85A), and remained significantly higher than baseline at the end of follow-up (D168) in Group A ($p=0.003$). A second dose of ChAdOx1 85A did not boost these IFN- γ responses in Group C, however they were significantly boosted with MVA85A vaccination at D56 (Group B) and D119 (Group C) ($p=0.0005$ at D63 (Group B) and D126 (Group C), IFN- γ responses remained significantly higher than at baseline at the end of the study ($p=0.005$ for Group B D224 and $p=0.001$ for Group C D287). No differences were detected in the magnitude of the MVA85A-boosted IFN- γ responses between Group B and Group C one week post-MVA85A ($p=0.31$). Polyfunctional CD4 and CD8 + T cells are detectable after ChAdOx1 85A and MVA85A vaccinations.

5.2. Goal

Our goal is to identify a TB vaccination regimen that will induce strong protective immune responses against tuberculosis in a tropical endemic setting.

5.3. Hypothesis

Our hypothesis is that a prime-boost regimen of ChAdOx1 85A – MVA85A will have greater immunogenicity than BCG revaccination among Ugandan adolescents who were BCG vaccinated at birth, and comparable immunogenicity to that observed in European adults.

5.4. Risks and Benefits

5.4.1. Potential risks

The potential risks to volunteers in this trial include risks associated with:

1. Venepuncture

Localised bruising and discomfort can occur at the site of venepuncture. Infrequently fainting may occur. The total volume of blood drawn over a 6-month period will be 160mL, which should not compromise these otherwise healthy volunteers.

2. Vaccination

ChAdOx1 85A has been administered to 42 healthy UK adults with no SAEs or safety concerns. MVA85A has now been administered to over 2500 healthy human individuals with one possible serious adverse reaction (SAR). BCG is a licensed vaccine which has been administered to millions of people. The potential known adverse events associated with vaccination are:

Local reaction from IM vaccination

The typical local reaction as a result of IM injection is temporary pain, redness and swelling at the site of the injection.

Local reaction for intradermal (ID) vaccination

BCG vaccination or revaccination usually causes local scarring and occasionally an abscess and regional lymphadenopathy [52].

Systemic reactions

Constitutional influenza-like symptoms such as fatigue, headache, malaise, feverishness, and muscle aches can occur with any vaccination and last for 2-3 days. In the case of MVA85A, and ChAdOx1 85A these are usually mild to moderate in severity, and transient. Following ChAdOx1 85A vaccination in TB034, transient lymphopenia and neutropenia was seen in some volunteers; all spontaneously resolved. Similar mild to moderate transient abnormalities of leukocyte parameters have been previously noted in other adenovectored vaccine studies [24, 53].

Presyncopal and syncopal episodes may occur at the time of vaccination which rapidly resolve. As with any other vaccine, immune mediated reactions that can lead to organ damage may occur. For influenza vaccines an excess of approximately 1 Guillain-Barré syndrome case per million persons immunised has been observed. No cases were observed in people under 45 years of age. However, this has never been seen with the ChAdOx1 85A or MVA85A vaccines or vaccines containing any of its components. In immunocompromised people, BCG vaccination can cause disseminated disease [54, 55].

Allergic reactions

Allergic reactions from mild to severe may occur in response to any constituent of a medicinal product's preparation. Anaphylaxis is extremely rare (less than 1 in 1000 people) but can occur in response to any vaccine or medication.

5.4.2. Potential benefits

Volunteers are not expected to benefit directly from participation in this trial. Volunteers will gain some information about their general health as a result of the screening history, examination, blood tests, and urine tests. Volunteers found to have a previously undiagnosed condition thought to require further medical attention will be referred appropriately for further investigation and treatment, with their permission.

It is hoped that their contribution will further the development of a safe and successful vaccine for TB and our knowledge about TB infection and protection.

6. OBJECTIVES AND OUTCOME MEASURES

Objectives	Outcome Measures	Timepoint(s) of evaluation of this outcome measure
Primary Objective To evaluate the safety and immunogenicity of ChAdOx1 85A – MVA85A prime-boost vaccination in Ugandan adolescents	Actively and passively collected data on adverse events	All Adverse Events (AEs) from day 0-28 post vaccination Serious Adverse Events (SAEs) throughout follow up
	T-cell Interferon- γ ELIspot response to antigen 85A	ELIspot spot-forming counts per 1×10^6 peripheral blood mononuclear cells (PBMCs) at day 14 for groups 1-4 ELIspot spot-forming counts per 1×10^6 peripheral blood mononuclear cells (PBMCs) at day 63 for groups 5 and 6 Area under the curve (AUC) analysis of immunogenicity (days 0-168 for groups 1-4; days 0-168 for groups 5 and 6)
Secondary Objective To further characterise immunogenicity of ChAdOx1 85A – MVA85A prime-boost vaccination in Ugandan adolescents	Antibody response to antigen 85A Exploratory immunology including ELIspot response to BCG, flow cytometry, gene expression, and mycobacterial killing assays	Screening and follow up visits as shown in Schedule of Visits, section 3
Tertiary Objectives 
 
To compare the response to ChAdOx1 85A – MVA85A prime-boost vaccination with the response to BCG revaccination in Ugandan adolescents 
To compare the response to ChAdOx1 85A – MVA85A prime-boost vaccination in Ugandan adolescents with the response in Oxford adults 
To investigate pre-immunisation epidemiological and immunological characteristics associated with the immune response induced by ChAdOx1 85A – MVA85A prime-boost vaccination in Ugandan adolescents 	T-cell Interferon- γ ELIspot response to antigen 85A Antibody response to antigen 85A, exploratory immunology including T cell ELIspots, flow cytometry, gene expression, and mycobacterial killing assays	Primary outcomes for these analyses will be antigen 85A specific ELIspot spot-forming counts per 1×10^6 peripheral blood mononuclear cells (PBMCs) at day 63 from the first vaccination and ELIspot AUC analysis Additional outcomes using data from follow up visits as shown in Schedule of Visits, section 3 Screening and follow up visits as shown in Schedule of Visits, section 3

Table 4. Objectives and Outcome Measures

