Timeline (weeks)*		0		2	4	8-52	9-53	12-56	20-64	32-76
Time windows (days)	-90 to -7		+1	+3	+5	+5	+1	+5	+5	+14
Vaccination, ChAdOx1 85A or BCG		x								
Vaccination, MVA85A [§]						x [§]				
Inclusion/exclusion criteria	x	x								
Review contra- indications	x	x				x				
Informed consent	x									
Medical history	x	(x)	(x)	(x)	(x)	(x)	(x)	(x)	(x)	(x)
Physical examination	x	(x)	(x)	(x)	(x)	(x)	(x)	(x)	(x)	(x)
Vital signs	x	x	x	x	x	x	x	x	x	x
Urinalysis	x									
β-HCG urine test (female only)	x	x				x				
Stool parasitology	x	x	x							x
Anthelminthic treatment									x	
Local & systemic events/reactions		x	x	x	x	x	x	x	x	x
Diary cards provided		x				x				
Diary cards collected				x			x			
Biochemistry (4mL)**/***	x			x		x	x			
HBV, HCV, HIV (6mL)	x									
Haematology: full blood count and storage (2mL)	x		x	x		x	x		x	x
Mansonella perstans (1mL)***	x									x
Malaria RDT/slide; PCR (1mL)	x	x***		x	x	x		x		x
Assessments of immunogenicity and exploratory immunology incl ELISpot (10-20mL)****	x	x	x	x	x	x	x	x	x	x
Gene expression (2mL)	x		x							
Blood vol (mL)	26	10	16	28	5	13	28	5	5	24
Cumulative blood vol (mL)	26	36	52	80	85	98	126	131	136	160

X Event scheduled to occur

(X) If considered necessary, emphasising any complaint or change in medications

* Timeline is approximate only, as exact timings (\pm windows periods) of visits relate to the actual (not intended) date of the previous visit

§ Group 5 only

** Urea & electrolytes, liver function tests

*** Repeated on vaccination day if delay from screening is more than 28 days

**** Exploratory immunology blood volume will be guided by guidelines from Harvard Mass General, where a maximum of 3ml/kg body weight is taken at any one time point and not more than 3ml/kg is taken over any 8 week period (ref http://www.drgreene.com/21_1616.html.) These guidelines have been followed in previous

studies vaccinating adolescents and children with MVA85A (in South Africa [1]). The total blood volume planned is 98 ml over the initial intensive sampling period of 8 weeks. Revision of sample volumes based on weight will only be required for children who weigh less than 33 kg; the average weight of children aged 11 is expected to be greater than 35kg, with greater weights for older children.

a Participants will have variable follow up days depending on whether they were enrolled before or after the COVID 19 lockdown

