11. STATISTICS

This is primarily an exploratory immunogenicity and safety trial with descriptive endpoints.

Adverse events will be listed and summarised by type of AE, frequency, severity and trial group.

The sample size (12 participants for dose escalation and age de-escalation, 60 participants [30 in each arm] for the randomised trial) has been determined by the number of doses of ChAdOx1 85A available for this study. The following are the considerations regarding sample size for the randomised component of the trial. The primary outcome is the IFN- γ ELIspot response to antigen 85A at week 9 which is measured in spot forming counts per 1×10^6 peripheral blood mononuclear cells (PBMCs). Assuming a standard deviation of $0.4 \log_{10}$ sfc/ 1×10^6 PBMC (spot forming counts/ 1×10^6 peripheral blood mononuclear cells) in the peak Ag85A response, our study will have over 80% power to detect a difference of $0.29 \log_{10}$ in sfc/ 10^6 PBMC with $p < 0.05$. This is comparable to the difference that was observed between the response to human adenovirus vectored TB vaccine candidate Aeras 402 alone (Day 14 post Aeras) and Aeras 402 with MVA85A boost (Day 7 post MVA boost) [21], or between BCG (Day 28) and MVA85A alone (Day 7) in UK subjects [62], and hence a reasonable difference to expect between BCG and ChAdOx1 85A-MVA85A (aim 2).

For outcomes that are approximately normally distributed or normalised by log-transformation, differences in means will be presented together with 95% confidence intervals and p-values from unpaired t-tests. For non-normally distributed outcomes, the difference in medians between the two groups will be presented along with its 95% confidence intervals, and p-values from Wilcoxon ranksum tests.

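### The days 0–168 ELISpot AUC for groups 5 and 6 does not fit the widened MVA85A boost window, and the day-63 label should be tied to Visit 7

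*Combined protocol and SAP*

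**What the plan says.** Table 4 (Section 6) lists two ELISpot outcomes under the primary objective for groups 5 and 6: counts in "peripheral blood mononuclear cells (PBMCs) at day 63 for groups 5 and 6", and an AUC over "days 0-168 for groups 1-4; days 0-168 for groups 5 and 6". The tertiary row, which covers the comparisons with BCG and with Oxford adults, uses the antigen 85A count "at day 63 from the first vaccination and ELIspot AUC analysis". Section 11 gives the primary outcome as the "ELIspot response to antigen 85A at week 9".

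The current schedule is built differently. Table 1.2 (Section 3.3), Section 7.9 and Section 8.4.2 (booster immunisation) allow the boost on days 56–365 for participants enrolled before the lockdown. The next visits come 7 days, 28 days, 3 months and 6 months after it. New enrolees are boosted on day 56 and seen on days 63, 84, 140 and 224. Group 6 attends on the same shifted dates to give samples only. A footnote to both schedules says that exact timings "of visits relate to the actual (not intended) date of the previous visit".

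Other current text gives different boost timing: day 56 in the Synopsis (Section 3.1), and days 56–140 in Section 8.4.3.

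**The concern.** Table 4 and Section 11 count from the first vaccination, while the visits after Visit 5 are counted from the boost. Neither place re-anchors the outcomes or gives a rule for late boosts. The last two amendments list changes to Sections 3.3, 7.9 and 8.4.2 only, which explains how the mismatch arose.

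If the AUC is computed as written, two group 5 participants with identical responses to each vaccine get different values because their boost dates differ. The group summary is then not a measure of the prime-boost regimen. It would still be reported under the primary objective, and an ELISpot AUC also feeds the comparisons with BCG and with Oxford adults. The matching Oxford prime-boost group was boosted on day 56 (Section 5.1.5).

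**Working it through.** **The plan's own figure.** Section 11 states over 80% power with 30 per arm, SD 0.4 log10 and difference 0.29 log10. Taking p < 0.05 as two-sided: 0.29 / (0.4 × √(2/30)) = 2.808; 2.808 − 1.960 = 0.848; power = 80.2% (78.8% by the noncentral t). The figure reproduces, apart from this small t correction. It concerns the week-9 count, not the AUC, so it is not evidence on this point either way.

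**Inputs.** AUC window: days 0–168 (Table 4). Boost day B: 56–365 (Sections 3.3, 7.9, 8.4.2), or 56–140 (Section 8.4.3). Post-boost visits: B+7, B+28, B+84, B+168 (Section 7.9; 140 − 56 = 84 and 224 − 56 = 168).

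**Samples inside the window.** A visit counts if its day is at most 168. So B+84 counts for B ≤ 84, B+28 for B ≤ 140, B+7 for B ≤ 161, and B+168 never counts.

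| Boost day | Permitted days | Post-boost samples by day 168 |
|---|---|---|
| 56–84 | 29 | 3 |
| 85–140 | 56 | 2 |
| 141–161 | 21 | 1 |
| 162–365 | 204 | 0 |

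The rows sum to 310 days. With the 56–140 limit only the first two rows apply. Visit windows, read as ±5, ±5 and ±1 days, move the cut-offs to 79–89, 135–145 and 160–162.

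**Post-boost time inside the window** is max(0, 168 − B): 112 days for B = 56, 28 for B = 140, and 0 from B = 168. If Visit 6 itself falls after day 168, the only scheduled samples in the window, in either arm, are days 0, 2, 14 and 28. The other 140 of 168 days must be interpolated or extrapolated, and no rule is given.

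**The day-56 schedule.** No visit falls on day 168, so that value has to be interpolated over the 84 days between days 140 and 224. Groups 1–4 do have a day-168 visit (Table 1.1), so the window fits them.

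**The day-63 label.** Visit 7 is nominally day 63 only when B = 56; at B = 365 it is day 372. For a boost after day 63, day 63 is no scheduled visit and comes before the boost.

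**Size for one participant (illustration).** Assume level 1 before the boost and k = 1.95 (= 10^0.29, the Section 11 difference) after it, on the count scale.

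- Step response: AUC = min(B, 168) + k × max(0, 168 − B). B = 56: 56 + 1.95 × 112 = 274.4. B = 140: 140 + 1.95 × 28 = 194.6 (29% lower). B ≥ 168: 168.0 (39% lower).
- Excess halving every h days: AUC = 168 + 0.95 × (h / ln 2) × (1 − 2^(−(168−B)/h)) for B ≤ 168. With h = 28: 204.0, 187.2 and 168.0 for B = 56, 140 and 168 or later (8% and 18% lower). With h = 56: 225.6, 190.5 and 168.0 (16% and 26% lower).
- Log10 scale, step of 0.29 on an assumed baseline of 2–3 log10: about 5–7% and 6–9% lower.

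**The case against.** Section 11 says "This is primarily an exploratory immunogenicity and safety trial with descriptive endpoints" and gives the AUC no power or decision rule of its own. At most, its general paragraph on t-tests and rank-sum tests covers it. This stands and limits the harm to interpretation, but a descriptive summary must still describe the intended quantity.

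The intended ELISpot visit is hardly in doubt. Section 11 takes its benchmark from "Aeras 402 with MVA85A boost (Day 7 post MVA boost", and the Oxford trial, with boosts on days 56 and 119, compared "responses between Group B and Group C one week post-MVA85A". That makes the day-63 part a wording correction. A reader might infer that late-boosted participants would be sampled before their boost; the documents do not support that.

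A reader might also infer that two-thirds of group 5 lack post-boost data, since 204 of 310 permitted days (66%) leave no sample in the window. That is a share of days, not of participants, and new enrolees keep day 56.

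A natural remedy would be to use only the boost-anchored segment from Visit 6 to Visit 9. For the comparison with BCG this would tilt towards group 5: in group 6 that segment starts 56–365 days after BCG and omits the early BCG response. Section 11 itself benchmarks BCG at day 28. This objection stands and shapes the fix.

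**Conclusion.** The point holds and should be fixed. As written, the 0–168 AUC for groups 5 and 6 depends on boost date and mixes full, truncated and prime-only curves. It contains 3, 2, 1 or 0 scheduled post-boost samples, or 3 or 2 if the day-140 limit applies. These counts assume nominal visit days.

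The effect on group results is unknown, because the documents give neither the number delayed nor their boost days. For one participant, the reduction against a day-56 boost is roughly 8–29% with a day-140 boost and 18–39% from day 168. This assumes a 1.95-fold rise that either persists or halves every 28 or 56 days. It is smaller on the log scale, and Table 4 does not state the AUC scale.

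A reader might infer a loss of power for the primary ELISpot outcome. The documents do not support that. Nor do they show that SD 0.4 and difference 0.29 hold across the wider boost intervals, so no claim about power is made in either direction.

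**What to change.** 1. In Table 4 (primary and tertiary rows) and Section 11, define the ELISpot outcome as the antigen 85A response at Visit 7: 7 days after MVA85A in group 5, and 7 days after the Visit 6 attendance in group 6.
2. For groups 5 and 6, replace the 0–168 AUC with the sum of two segments: day 0 to Visit 5 (28 days) and Visit 6 to Visit 9 (84 days). Use the trapezoid rule on actual sampling days, divide each area by the actual segment length, and combine the two with weights 28 and 84, so that every total refers to 112 days. State the scale. Report both segments in both arms, and do not use the Visit 6 to Visit 9 segment alone as the primary comparison with BCG.
3. Add a sensitivity analysis limited to participants in both arms on the day-56 schedule, using a day 0–140 AUC, which ends at a scheduled visit.
4. The sponsor must reconcile the boost timing in Sections 3.1, 3.3, 7.9, 8.4.2 (booster) and 8.4.3. That decides which rows of the table above apply.

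**Cost.** Wording changes and one extra analysis, using visits already scheduled. The new AUC leaves out the time from day 28 to Visit 6 and everything after Visit 9. Time since BCG at Visit 6 still varies in group 6. Comparability with the 0–168 AUC of groups 1–4 is reduced, and the sensitivity analysis may have fewer participants.

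One check is needed first. Table 1.2 states 10–20 mL for immunology at every visit. Subtracting the other listed tests from each visit total leaves 5 − 1 = 4 mL at Visit 5, 13 − 7 = 6 at Visit 6, 5 − 1 = 4 at Visit 8 and 5 − 2 = 3 at Visit 9. The sponsor should confirm that these volumes support ELISpot. The current AUC depends on the same visits wherever they fall inside its window.

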The follow up period for those enrolled after the COVID 19 lockdown will be 24 weeks after first vaccination and 24 weeks after booster vaccination for those enrolled before the lockdown in accordance with findings from previous studies in which adequate safety data and reliable markers of immunogenicity have been obtained in this time interval. Due to the nearly three months COVID-19 lockdown and halting of trial activities, participants who had already been enrolled in the trial by that time will have a later MVA85A vaccination boost ranging up to **52** weeks (instead of 8 weeks) after initial vaccination with ChAdOx1 85A. Their subsequent follow up visits will be at day 7, day 28, 3 months and 6 months post boost vaccination. Their follow up visits will therefore fall within the following ranges of **63-372**, **84-393**, **140-449** and **224-533** days. Newly enrolled participants into Group 5 will follow the original schedule of the MVA85A boost at day 56 and subsequent follow up visits on days 63, 84, 140 and 224. All follow up visits will last approximately 15 to 30 minutes. Most of the participants are currently in secondary school which are either day or boarding. For logistical and time management purposes as well as to minimize disruption of their studies, participants in boarding schools will be offered the option of having follow up visits done at the school premises. A qualified clinician and nurse will visit the school with the necessary supplies and equipment for the visit on the said date. The clinician will examine and assess the participant while the nurse will draw blood and collect the relevant samples for that visit. The trial team will seek permission and a formal introductory letter from the district education officials to the school management for access to the schools. The team will secure suitable space for these activities. The team will ensure the participant

is in a good health condition before departing from the school. The study contact phone number will be availed to the school to follow up on any concerns.

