8.4.1. Subsequent visits

All volunteers will be asked to attend as per the Schedule of Visits and Procedures in section 3. On visits other than for vaccination the volunteers will be assessed for local and systemic adverse events, using paper diary cards, interim history, physical examination and blood tests at the time-points indicated in the Schedule of Visits and Procedures (Section 3). Blood will also be taken for assessments of immunogenicity and exploratory immunology analysis. These follow up visits may be done at school (see section 7.9).

8.4.2. MVA85A booster immunisation.

Volunteers in group 5 will be asked to attend between day 56 and day **365** for booster immunisation with MVA85A [volunteers in group 6 will also be asked to attend on this date, but only to provide the samples indicated]. For participants who were enrolled in the trial prior to the COVID-19 lockdown, this boost visit will fall between day 56 and day **365** after enrolment into the trial while for newly enrolled participants, the boost will be done on day 56.

For group 5, before the MVA85A vaccination, the health of the volunteer will be reviewed. Pulse, blood pressure and temperature will be observed and if necessary, a medical history and physical examination may be undertaken to determine need to postpone booster vaccination. For girls, a pregnancy test will be repeated. If the volunteer is well and the pregnancy test is negative MVA vaccination will be administered at 1×10^8 pfu.

Group 5 volunteers will be provided with a diary card and instructed in its use as described above.

Diary cards will be collected two weeks after ChAdOx1 85A and one week after MVA85A as these intervals correspond to the optimal time points for assessing the initial response to the two vaccines.

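### Tertiary objective 2 sets no limit on prime-boost interval: group 5 boosts may fall as late as day 365, while the only one-prime Oxford arm was boosted at day 56

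*Combined protocol and SAP*

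**What the plan says.** - **Objective.** Table 4 (section 6), tertiary objective 2, compares the response to ChAdOx1 85A – MVA85A "prime-boost vaccination in Ugandan adolescents with the response in Oxford adults". It names neither a subset of group 5 nor an arm of the Oxford study. Section 5.3 states the matching hypothesis: "comparable immunogenicity to that observed in European adults". No margin is given.
- **Outcome.** The primary outcomes for the tertiary comparisons are antigen 85A ELISpot counts "at day 63 from the first vaccination and ELIspot AUC analysis". Elsewhere in Table 4, the AUC for groups 5 and 6 covers days 0 to 168.
- **Boost timing in group 5.** Section 7.9 says that those already enrolled at lockdown "will have a later MVA85A vaccination boost ranging up to 52 weeks (instead of 8 weeks". Section 8.4.2 (MVA85A booster immunisation) says that for them "this boost visit will fall between day 56 and day 365 after enrolment into the trial". Later enrolees keep the planned interval: "Newly enrolled participants into Group 5 will follow the original schedule of the MVA85A boost at day 56".
- **Oxford comparator.** Section 7 identifies the Oxford study as TB034. Table 3 shows one arm with a single ChAdOx1 85A dose followed by MVA85A: Group B, n=12, boosted at day 56. Group C (n=12) had two ChAdOx1 85A doses before its boost. Section 5.1.5 reports responses "significantly boosted with MVA85A vaccination at D56 (Group B) and D119 (Group C".
- **Analysis.** Section 11 offers unpaired t-tests or rank-sum tests. It gives no method for the Oxford comparison and no stratification, adjustment or subset by interval.

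**The concern.** The amendment changed the regimen that part of group 5 receives, but objective 2 and the hypothesis were left as they were. A one-prime regimen with an interval beyond day 56 can occur only among the Ugandan participants. The comparison is with a completed external study, so randomisation does not balance anything in it. If the interval affects the response, a pooled comparison attributes that effect to population. Depending on its sign, it could create an apparent Uganda–Oxford difference or hide a real one and so favour a conclusion of comparability.

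The stated outcomes add a second problem. If day 63 is counted from the first vaccination, a participant boosted after that day has no boosted response to measure.

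**Working it through.** **1. Sampling.** Table 1.2 has visits at day 28, at the boost visit (days 56–365), and then at visit 7 (days 63–372), which is 7 days after boost.
- Boost at day 56: day 63 and visit 7 coincide.
- Boost after day 63: day 63 precedes the boost. No visit is scheduled between day 28 and the boost visit, so no day-63 sample is planned either. Table 4 and visit 7 describe different measurements.
- Boost after day 168: the boost lies outside the 0–168 AUC window, whereas Group B's day-56 boost would lie inside the same window.

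**2. The plan's own figure.** Section 11 gives 30 per arm, SD 0.4 log10, difference 0.29 log10 and over 80% power. With two-sided alpha 0.05 (sidedness is not stated): SE = 0.4 × √(2/30) = 0.103, and 0.29/0.103 − 1.96 = 0.85, so power is 80.2% (78.8% from the t distribution). This reproduces the figure, which concerns group 5 versus group 6. No figure is given for objective 2.

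**3. Shift from pooling.** If k of 30 are boosted late and the interval changes the mean response by δ log10, the group 5 mean moves by (k/30)·δ. The documents give neither k nor δ, so all values below are assumptions. With 30 versus 12, SE = 0.4 × √(1/30 + 1/12) = 0.137. The last column is the chance of a two-sided p below 0.05 when the populations do not differ (nominal 5%; normal approximation, SD 0.4 throughout).

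| Share late | δ (log10) | Shift (log10) | Rejection rate |
|---|---|---|---|
| 0.25 | 0.10 | 0.025 | 5.4% |
| 0.25 | 0.20 | 0.05 | 6.5% |
| 0.50 | 0.20 | 0.10 | 11.3% |
| 0.50 | 0.40 | 0.20 | 31.0% |

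The sign of δ is unknown, so the shift can go either way.

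**4. What TB034 can say about interval.** For 12 versus 12 at SD 0.4, the difference detectable with 80% power is 0.4 × √(2/12) × (1.96 + 0.84) = 0.46 log10. The absence of a detected difference between Groups B and C therefore leaves room for every δ in the table.

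**5. Price of matching.** Difference detectable with 80% power against 12 Oxford adults (t distribution, SD 0.4): 0.39 log10 with all 30, 0.42 with 22, 0.45 with 15 and 0.54 with 8.

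**The case against.** The strongest reply uses the protocol's own evidence. Section 5.1.5 reports no detected difference between Groups B and C one week after MVA85A (p=0.31), although their boosts came at day 56 and day 119. It adds that the second ChAdOx1 85A dose did not raise the response, which weakens the argument that Group C is a different regimen. This does mean that nothing in the documents points to an interval effect. It does not exclude one: each arm had 12 people, Group C still had an extra prime, and day 119 is far short of day 365.

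The number affected may also be small. Anyone boosted on schedule before the lockdown has the matching interval, as does everyone enrolled afterwards. At the low end of the assumed range the bias is negligible. Age, country and infection exposure differ from Oxford whatever the interval, so matching removes one confounder among several. The objective is tertiary and section 11 calls the trial exploratory and descriptive. All of this stands, and it limits the importance of the point without answering it.

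Two stronger readings go beyond the text. A reader might infer that the plan prescribes all of group 5 against Group B. Table 4 specifies neither; that is only the natural reading, because no restriction is stated and only Group B matches the regimen. A reader might also compare a 0.20 log10 shift with the 0.29 log10 in section 11 and call it two-thirds of the relevant difference. That 0.29 is tied to the BCG contrast, and objective 2 has no relevance margin.

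**Conclusion.** The point holds as a gap in specification that should be closed before analysis. As written, objective 2 can mix prime-boost intervals of 8 to 52 weeks on the Ugandan side with a comparator arm boosted at 8 weeks, and its day-63 and AUC outcomes do not capture the boosted response of those boosted late. The confounding is partial, because participants boosted at day 56 share the Oxford interval.

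The size is unknown. The range of 0.025 to 0.20 log10 rests entirely on assumed values (a quarter to a half boosted late, interval effect 0.10 to 0.40 log10) and on the plan's SD of 0.4. A reader might infer that the hypothesis of comparability with European adults cannot be assessed at all. The documents do not support that: a matched-interval comparison is available from data already planned, though it remains non-randomised.

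The latest boost day is itself inconsistent: day 56 in the synopsis, day 140 in section 8.4.3, and day 365 in sections 7.9 and 8.4.2. These must be reconciled. Every version that allows a delay leads to the same conclusion on interval; a boost beyond the AUC window arises only under the day-365 text.

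**What to change.** In Table 4 and section 11:

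1. Name TB034 Group B as the comparator for objective 2.
2. Reconcile the day-63 outcome with visit 7 of the schedule, so that the comparison is made 7 days after boost, and state how the AUC is handled when the boost falls late in or after the 0–168 day window.
3. Make group 5 participants boosted at day 56, within the visit window of Table 1.2, the main matched-interval comparison.
4. Report all of group 5, and the later-boosted participants by interval, as supporting description.
5. Base any statement of comparability with European adults on the matched set, and say that age, country and exposure remain confounded.

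This is analysis wording and needs no new data, since boost dates are recorded with the visits. Fixing the subset in advance also avoids choosing it after seeing results. The cost is fewer Ugandan participants and a wider confidence interval: a detectable difference of about 0.45 log10 with 15 matched participants, against about 0.39 with all 30.
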